5.4 CRITERIA FOR WITHDRAWAL

Patients will be informed that they have the right to withdraw from the trial at any time, without prejudice to their medical care, and that they are not obliged to state their reason(s). Any withdrawal must be fully documented in the eCRF and source documents, and should be followed up by the Investigator.

The Investigator may withdraw a patient at any time if this is considered to be in the patient's best interest.

If the study patient support program is prematurely discontinued, the primary reasons for discontinuation must be recorded in the appropriate section of the eCRF.

The Investigator/nurse will arrange for appropriate follow-up according to visit 2 for patients withdrawing from the study.

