6 INVESTIGATIONAL PATIENT SUPPORT PROGRAM AND OTHER TREATMENTS IN THE TRIAL

6.1 DESCRIPTION OF INVESTIGATIONAL PATIENT SUPPORT PROGRAM (MINSUPPORT PLUS)

MSP is a service from Merck AB which includes:

- Technical support for the RebiSmart device
- Personal coaching regarding treatment and understanding of the disease
- Lifestyle Guide
- Web support (personal health records)

The patient is assigned a personal nurse/coach and a personal health counselor/advisor. The first two services described below are performed by the personal nurse and the third service by the personal health counselor.

1. Technical support

The personal nurse provides technical support for the RebiSmart device.

2. Treatment and understanding of the disease

The personal nurse supports and guides the patient in adherence to the prescribed Rebif® therapy, provides disease information and motivating support for the treatment of MS. The nurse checks the patient's understanding of the doctor's prescription, the administration of the medicine and makes continuous evaluation of patient's status, issues, and problems with regard to treatment using a set of questions in the patient's health record ("Hälsojournal").

This support is managed by;

- A set of telephone contacts with the patient; 1 registration call followed by 6 motivational calls during 12 months. The calls to the patients are booked 1-7 days in advance
- The telephone calls are supported by customized mailings and mobile text messaging to the patients

4. Lifestyle Guide

This support is provided by a personal health counselor. The purpose of the Lifestyle Guide is to inspire and motivate a choice of lifestyle(s) in order to improve health and wellbeing. The Lifestyle Guide is based on The Swedish National Board of Health and Welfare's National Guidelines for Methods of Preventing Disease. These guidelines provide recommendations for methods of preventing disease by supporting patients in their efforts to change an unhealthy lifestyle habit. The Lifestyle Guide offers guidance in six areas; diet, exercise, stress management, smoking, sleep and alcohol. Counselling is individual, which means that the patient agrees with the lifestyle counsellor which areas to focus on and in which order. Most people who start with lifestyle changes will end in 6-10 weeks (30). As our intention is to achieve long term change, the program runs during 12 months.

The Lifestyle Guide is managed by;

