- An Introductory questionnaire which concerns different areas that affects health. The patient may also, in the questionnaire, indicate their willingness for change in each area (judging on a scale of 1 to 10).
- 6 motivating conversation with the personal health counselor.
 - The first conversation includes an initial analysis of individual needs and goal formulation based on the completed questionnaire. All patients will be offered stress management regardless of the result of the questionnaire as well as other support based on the analysis of individual needs.
 - The patients will formulate their own goals. The patient's goals and goal fulfillment are important in the process of change.
 - Five follow-up and motivating conversations will be distributed over a year.

3. Webb Support

The patient has access to two web-based personal health records, which can be adapted individually for optimal support:

- One managed by the personal nurse for coaching of treatment and understanding of the disease documented in a Health Record (“Hälsojournal” in Swedish)
- One managed by the personal health counsellor for coaching of life style documented in a Health Diary (“Hälsodagbok” in Swedish)

The information reported by the patient is used to provide individual feedback and to determine the content of the coaching conversations.

Health Solutions AB

MSP will be provided by Health Solutions AB, a registered healthcare company active in two areas; diagnosis-specific patient support and patient support for lifestyle changes. Health Solution AB is located in Luleå, Sweden.

The coaching includes several different communication alternatives; telephone, e-mail, outbound text messaging, online chats, as well as the technical platform RealQ supporting the personal health records. The patient can contact the personal coaches via telephone, instant messaging or e-mail according to his or her own needs. All calls are documented in the health records. In addition, all incoming mails to the personal nurse are documented in the patient's health record (“Hälsojournal” in Swedish).

The calls are performed according to the Motivating Interviewing (MI) method and are individually adjusted for the patients’ need. The calls are coordinated with mail and mobile text messaging.

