6.2 ASSIGNMENT TO TREATMENT GROUPS

The patient will be randomized to one of two study arms (1:1):

Arm 1: Technical support for the RebiSmart device

Arm 2: Patient support program MSP

The randomization will be stratified for sex and severity of disease.

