6.4 METHOD OF BLINDING

At visit 1, the patients will complete all questionnaires (except for the Lifestyle questionnaire), i.e. before allocation to study arm which will be performed by Health Solutions during the first week. The questionnaires will be sent for data entry to a unit within Health Solutions which is separate to the unit providing the patient support. At 6 and 12 months the questionnaires will be sent out directly to the patients for completion and the patients will return completed questionnaires to the separate unit at Health Solutions for data entry. The entered data will be transferred to an external vendor for data management and statistics. Thus, the Investigator/Study nurse will be blinded with respect to study arms unless the patient actively reveals it to the Investigator/Study nurse. In the patient information the patients will be asked not to reveal which study arm they are allocated to.

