Severe: Significant impairment of functioning: the patient is unable to carry out usual activities.

Investigators must also systematically assess the causal relationship of AEs to Rebif using the following definitions. Decisive factors for the assessment of causal relationship of an AE to Rebif include, but may not be limited to, temporal relationship between the AE and Rebif, known side effects Rebif, medical history, concomitant medication, course of the underlying disease, trial procedures

- **Not related:** Not suspected to be reasonably related to Rebif. AE could not medically (pharmacologically/clinically) be attributed to Rebif under study in this clinical trial protocol. A reasonable alternative explanation must be available.
- **Related:** Suspected to be reasonably related to Rebif. AE could medically (pharmacologically/clinically) be attributed to Rebif under study in this clinical trial protocol.

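### Recording in the eCRF why a patient stopped the support programme discloses Arm 2 to site staff whom the blinding section treats as blinded, unless the patient has already told them

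*Protocol*

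**What the plan says.** Protocol section 5.4 (Criteria for Withdrawal): "If the study patient support program is prematurely discontinued, the primary reasons for discontinuation must be recorded in the appropriate section of the eCRF". The sentence is passive and does not say who makes the entry.

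Protocol section 6.2 defines the arms: "Arm 1: Technical support for the RebiSmart device" and "Arm 2: Patient support program MSP". Section 6.1 describes the programme (MinSupport Plus) and says that Health Solutions delivers it. On where contact with patients is logged, it says: "All calls are documented in the health records".

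Protocol section 6.4 (Method of Blinding) says that "the Investigator/Study nurse will be blinded with respect to study arms unless the patient actively reveals it", and adds: "In the patient information the patients will be asked not to reveal which study arm they are allocated to".

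On adverse events, section 7.3.1 makes the investigator grade severity and says: "Investigators must also systematically assess the causal relationship of AEs to Rebif". Under section 8.3.3 the nurse records adverse events at visit 2, and the proportion of patients with an event is compared between arms.

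**The concern.** An entry giving reasons for stopping the programme can arise only for a patient who was in it, so the entry identifies the arm. If the site makes the entry, the protocol itself requires information that discloses allocation to staff it otherwise treats as blinded.

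The disclosure is also one-sided. It touches only Arm 2 and, within Arm 2, only patients who disengaged. Any influence on how staff record or grade adverse events in those patients would have no counterpart in Arm 1. If a site protects the blind by not asking, the reasons for stopping the trial's intervention go unrecorded, and these are useful data.

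**Working it through.** The point rests on reading sections together. No figure stated in the plan carries it.

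**1. Does the programme in 5.4 mean Arm 2 only?** Sections 6.1 and 6.2 tie it to MinSupport Plus and to Arm 2. Section 2, on third-party providers, lists technical support and the support programme as alternatives. The ethical background in section 9 contrasts programme users with patients who do not get this support. All of these point to Arm 2.

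**2. Does the site complete the eCRF?** 5.4 does not say so, but the rest of the protocol does in effect:
- The investigator signs off the case report form (5.1).
- The investigator completes its adverse event section (7.3.3).
- Only the investigator can link eCRF data to the patient (9.3).
- The investigator makes and countersigns corrections (9.7).
- Health Solutions' stated data task is questionnaire entry (2), and those data are transferred separately (6.4).

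No section gives Health Solutions access to the eCRF or hides this item from site staff. That the site makes the entry is therefore a strong inference, not a stated fact.

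**3. Does the exception in 6.4 cover the entry?** It covers active disclosure by the patient. There are three cases:
- The patient volunteers that they stopped and why. The exception applies, and 5.4 and 6.4 are both met.
- The patient says nothing and the site asks. The site is then seeking what the patient was asked to withhold.
- The patient says nothing and the vendor tells the site. The arm is disclosed by someone other than the patient, which the exception does not cover.

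The conflict lies in the second and third cases.

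**4. Where does the information arise?** At Health Solutions, which makes and logs the calls. The source data listed for the site file in section 9.8 include withdrawal from the trial or from Rebif, but not stopping the programme.

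**5. Which outcomes are exposed?**
- MSIS-29, the primary endpoint: completed at baseline before allocation, then by the patient at months 6 and 12 and returned to a separate data-entry unit (6.4). Not exposed by this route.
- Working ability and patient satisfaction: the patient's own answers to fixed items (7.2). Staff enter them but do not rate them, so exposure is weak.
- Adverse events: recorded by the nurse, with severity and relatedness judged by the investigator. The proportion with events is compared between arms (8.3.3), and events are tabulated by arm and severity (8.6.4). This is the main exposure.

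**6. How many patients?** Planned Arm 2 size is 130 / 2 = 65. The protocol gives no rate of stopping the programme. For illustration only, assumed rates of 10%, 20% and 30% give 65 × 0.10 = 6.5, 65 × 0.20 = 13 and 65 × 0.30 = 19.5 patients. Any who had already told the site would have to be subtracted. In Arm 1 the count by this route is 0.

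**The case against.** The strongest reply is that 6.4 is conditional. A patient who leaves the programme may well tell the clinic, and the protocol accepts that disclosure. A reader might infer that the two rules can never both be followed. The documents do not support that, because the volunteered case satisfies both. What stands is that 5.4 makes the entry mandatory and has no provision for the patient who has not spoken.

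Second, the recorder is not named and the eCRF layout and access rights are not shown. That is why the site's role is an inference here. No section points the other way.

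Third, section 6.3.1 asks patients who stop Rebif to continue in the support programme without limiting this to an arm. On that loose usage the 5.4 item could cover support in either arm and would disclose nothing. The definitions in 6.1 and 6.2, and the contrasts in sections 2 and 9, weigh more, but the wording lowers certainty somewhat.

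Fourth, the harm is limited. Adverse event data rest on what patients report spontaneously (8.6.4), and relatedness is not among the three summary tables listed there. Both points are right. Relatedness is still a required judgement, and severity is tabulated by arm.

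Finally, a reader might take the 20% in section 8.1 as the share of Arm 2 that would be unblinded. It is an allowance for trial drop-out, used only to inflate the sample size (104 / 0.80 = 130), and says nothing about stopping the programme.

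**Conclusion.** The conflict between 5.4 and 6.4 is real but narrow. Where the patient has not volunteered it, a required eCRF entry discloses Arm 2 to staff described as blinded. This rests on two readings: that the programme in 5.4 is the Arm 2 programme, and that the site completes the item. Both are well supported, the second by inference.

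The size cannot be estimated from the protocol. It is some part of about 65 Arm 2 patients and no Arm 1 patients. The direction of any effect on adverse event data is also unknown. It would be wrong to infer bias in the primary result, or staff rating of working ability or satisfaction. The point merits an amendment because the remedy is cheap and keeps both the blind and the stopping data. It does not threaten the trial's main conclusion.

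**What to change.** Amend 5.4 so that the Health Solutions support unit records the date and primary reason for stopping support, in either arm, under the patient number. The unit sends these to the data-management vendor, and site staff do not see them until database lock. Remove the item from the site eCRF. The site then records study withdrawal and Rebif discontinuation only, on the same form in both arms.

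The cost is an edit to 5.4, the removal of one eCRF item, a standard form for stopping reasons and a small new data flow. The existing questionnaire transfer should not simply gain a field. Section 6.4 keeps the data-entry unit separate from the support unit, and stopping reasons arise in the latter, so this flow should stay separate too.

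If the sponsor prefers to keep the item at the site, 5.4 should name who records it, and 6.4 should state that site staff may be unblinded for patients who stop the programme.

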5.4.1 Premature Discontinuation of the Trial

In case of study discontinuation, all national regulatory procedures will be followed.

5.5 DEFINITION OF END OF TRIAL

For administrative and safety reporting purposes, the end of the trial will be defined as the date of the final clinical database lock. This provides for a single and conservative definition across all trial centres.

6 INVESTIGATIONAL PATIENT SUPPORT PROGRAM AND OTHER TREATMENTS IN THE TRIAL

6.1 DESCRIPTION OF INVESTIGATIONAL PATIENT SUPPORT PROGRAM (MINSUPPORT PLUS)

MSP is a service from Merck AB which includes:

- Technical support for the RebiSmart device
- Personal coaching regarding treatment and understanding of the disease
- Lifestyle Guide
- Web support (personal health records)

The patient is assigned a personal nurse/coach and a personal health counselor/advisor. The first two services described below are performed by the personal nurse and the third service by the personal health counselor.

1. Technical support

The personal nurse provides technical support for the RebiSmart device.

2. Treatment and understanding of the disease

The personal nurse supports and guides the patient in adherence to the prescribed Rebif® therapy, provides disease information and motivating support for the treatment of MS. The nurse checks the patient's understanding of the doctor's prescription, the administration of the medicine and makes continuous evaluation of patient's status, issues, and problems with regard to treatment using a set of questions in the patient's health record ("Hälsojournal").

This support is managed by;

- A set of telephone contacts with the patient; 1 registration call followed by 6 motivational calls during 12 months. The calls to the patients are booked 1-7 days in advance
- The telephone calls are supported by customized mailings and mobile text messaging to the patients

4. Lifestyle Guide

This support is provided by a personal health counselor. The purpose of the Lifestyle Guide is to inspire and motivate a choice of lifestyle(s) in order to improve health and wellbeing. The Lifestyle Guide is based on The Swedish National Board of Health and Welfare's National Guidelines for Methods of Preventing Disease. These guidelines provide recommendations for methods of preventing disease by supporting patients in their efforts to change an unhealthy lifestyle habit. The Lifestyle Guide offers guidance in six areas; diet, exercise, stress management, smoking, sleep and alcohol. Counselling is individual, which means that the patient agrees with the lifestyle counsellor which areas to focus on and in which order. Most people who start with lifestyle changes will end in 6-10 weeks (30). As our intention is to achieve long term change, the program runs during 12 months.

The Lifestyle Guide is managed by;

- An Introductory questionnaire which concerns different areas that affects health. The patient may also, in the questionnaire, indicate their willingness for change in each area (judging on a scale of 1 to 10).
- 6 motivating conversation with the personal health counselor.
 - The first conversation includes an initial analysis of individual needs and goal formulation based on the completed questionnaire. All patients will be offered stress management regardless of the result of the questionnaire as well as other support based on the analysis of individual needs.
 - The patients will formulate their own goals. The patient's goals and goal fulfillment are important in the process of change.
 - Five follow-up and motivating conversations will be distributed over a year.

3. Webb Support

The patient has access to two web-based personal health records, which can be adapted individually for optimal support:

- One managed by the personal nurse for coaching of treatment and understanding of the disease documented in a Health Record (“Hälsojournal” in Swedish)
- One managed by the personal health counsellor for coaching of life style documented in a Health Diary (“Hälsodagbok” in Swedish)

The information reported by the patient is used to provide individual feedback and to determine the content of the coaching conversations.

Health Solutions AB

MSP will be provided by Health Solutions AB, a registered healthcare company active in two areas; diagnosis-specific patient support and patient support for lifestyle changes. Health Solution AB is located in Luleå, Sweden.

The coaching includes several different communication alternatives; telephone, e-mail, outbound text messaging, online chats, as well as the technical platform RealQ supporting the personal health records. The patient can contact the personal coaches via telephone, instant messaging or e-mail according to his or her own needs. All calls are documented in the health records. In addition, all incoming mails to the personal nurse are documented in the patient's health record (“Hälsojournal” in Swedish).

The calls are performed according to the Motivating Interviewing (MI) method and are individually adjusted for the patients’ need. The calls are coordinated with mail and mobile text messaging.

MI refers to a counselling approach in part developed by clinical psychologists [name] R Miller, Ph.D. and [name], Ph.D. It is a client-centered, semi-directive method of engaging intrinsic motivation to change behaviour by developing discrepancy and exploring and resolving ambivalence within the client (31). This interview method aims to increase the individual’s inner motivation for change and to strengthen his or her commitment to implementing change.

Schematic overview of coaching

The timing of the respective coaching of the personal nurse and personal health counselor is presented in the table below.

Time for call from patient inclusion		MinSupport	Lifestyle Guide
Month	Week	Personal Nurse	Personal Health Counselor
1	1	Registration call	Call 1
	2		Call 2
	3	Call 1	
2	2		Call 3
	3	Call 2	
3	2		Call 4
	3	Call 3	
5	2		Call 5
	3	Call 4	
8	3	Call 5	
9	2		Call 6
11	3	Call 6	
No of calls		7	6

6.2 ASSIGNMENT TO TREATMENT GROUPS

The patient will be randomized to one of two study arms (1:1):

Arm 1: Technical support for the RebiSmart device

Arm 2: Patient support program MSP

The randomization will be stratified for sex and severity of disease.

6.3 CONCOMITANT MEDICATIONS

Concomitant medication is defined as all other pharmaceutical therapy administered during the study.

6.3.1 Required Medications

Treatment with Rebif® 22/44 mcg as administered by the RebiSmart device and in accordance to the SPC (see Appendix I). The decision to prescribe Rebif® must have been made independently of and prior to considering inclusion into this study.

Patients discontinuing treatment with Rebif® due to any reason during the study period should continue assessments, participation in the support program and perform final visit. The reason for discontinuing Rebif® must be recorded in the eCRF. These patients will be included in the Intention-To-Treat (ITT) analysis and be excluded from the per protocol (PP) analysis.

6.3.2 Permitted Medications

Any medication considered necessary for the patient's welfare, may be given at the discretion of the Investigator.

6.4 METHOD OF BLINDING

At visit 1, the patients will complete all questionnaires (except for the Lifestyle questionnaire), i.e. before allocation to study arm which will be performed by Health Solutions during the first week. The questionnaires will be sent for data entry to a unit within Health Solutions which is separate to the unit providing the patient support. At 6 and 12 months the questionnaires will be sent out directly to the patients for completion and the patients will return completed questionnaires to the separate unit at Health Solutions for data entry. The entered data will be transferred to an external vendor for data management and statistics. Thus, the Investigator/Study nurse will be blinded with respect to study arms unless the patient actively reveals it to the Investigator/Study nurse. In the patient information the patients will be asked not to reveal which study arm they are allocated to.

